Attachment 17a.

Medical Condition	Record Located (Comments)	
g. Liver disease?	Yes (Please specify diagnosis) No	
h. Kidney disease?	Yes (Please specify diagnosis) No	
i. Diabetes?	Yes (Please specify diagnosis) No	
j. Gestational diabetes?	Yes No	
j. Osteoarthritis?	Yes (Please specify diagnosis) No	
k. Osteopenia or Osteoporosis? Yes (Please specify diagnosis) No		
I. Ulcerative colitis?	Yes No	
m. Rheumatoid arthritis?	Yes No	
n. Autoimmune disease? (i.e. Lupus, Multiple sclerosis, Emphysema, Fibromyalgia, Celiac Disease, Crohn's Disease)	Yes (Please specify) No	
o. Endometriosis?	Yes No	
p. Asthma? Yes No		
q. Cancer?	. Cancer? Yes (Please specify) No	
r. Other cancer?	Yes (Please specify) No	

Multi-site Study Medical Record Abstraction Form Child

Form Approved OMB No. 0923-XXXX Exp. Date xx/xx/201x

ATSDR estimates the average public reporting burden for this collection of information as 20 minutes per response, including the time for reviewing instructions, searching existing data/information sources, gathering and maintaining the data/information needed, and completing and reviewing the collection of information. An agency may not conduct or sponsor, and a person is not required to respond to a collection of information unless it displays a currently valid OMB Control Number. Send comments regarding this burden estimate or any other aspect of this collection of information, including suggestions for reducing this burden to CDC/ATSDR Information Collection Review Office, [name]; ATTN: PRA (0923-xxxx).

Medical Record Abstraction Form - Child

Study ID: []	Participant Name: []	Date of Birth://	SSN: xxx-xx-xxxx
--------------	----------------------	------------------	------------------

The person named above, or his or her legal representative, has authorized you to release his or her medical records to ATSDR/[insert institution name] for research purposes. Please check If you have a record that a doctor or other health care provider diagnosed or is treating any of the following medical conditions.

Please fill out the table below. Circle appropriate response and specify requested details as directed. Thank you.

		Year of
Medical Condition	Record Located (Comments)	Diagnosis or
		Treatment
a Allergies?	Yes (Please specify diagnosis)	
	No	
h Atonic dormatitic/oczoma2	Yes	
	No	
c Asthma?	Yes	
C. Astima:	No	
d Rhinitis?	Yes	
u. minus:	No	
	Yes	
e. High cholesterol?	No	
f Thuroid discoso?	Yes (Please specify diagnosis)	
	No	

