11	7.	Immune response including prevalence of hypersensitivity-related outcomes (e.g., asthma, atopic
12		dermatitis; higher levels of immunoglobulins (IgG, IgA and IgM) and lower antibody responses to
13		rubella, mumps, and diphtheria vaccines).
14	Neuroo	developmental outcomes (lower intelligence quotient (full scale IQ), attention-deficit and
15	hypera	ctivity disorder (ADHD).
16	For adu	ults (aged \geq 18 years), the Multi-site Study will evaluate the following main hypotheses.
17	Higher	serum levels of PFOA, PFOS, PFHxS, or other PFAS are associated with:
18	1.	Lipids (higher total cholesterol, low-density lipoprotein and triglycerides) and a higher prevalence
19		of hypercholesterolemia).
20	2.	Higher prevalence of coronary artery disease and hypertension (including hypertensive disorders
21		of pregnancy).
22	3.	Renal function (higher level of uric acid and a higher prevalence of hyperuricemia, lower
23		estimated glomerular filtration rate (eGFR)) and higher prevalence of kidney disease.
24	4.	Glycemic parameters (glucose, insulin, glycosylated hemoglobin (HbA1c), auto-antibodies (GAD-
25		65 and IA-2), C-peptide, pro-insulin) and diabetes (type 1 and 2).
26	5.	Differences in thyroid hormones (thyroid stimulating hormone (TSH), TT4, FT4, and TT3), and
27		higher prevalence of hypothyroidism/ hyperthyroidism.

1	6.	Liver function/damage biomarkers (alanine transaminase (ALT), γ -glutamyltransferase (GGT),
2		direct bilirubin, cytokeratin-18 (CK-18)) and liver disease.
3	7.	Higher prevalence of osteoarthritis and osteoporosis.
4		
5	8.	Higher prevalence of endometriosis.
6	9.	Measures of immune response and inflammation (serum levels of IgA, IgE, IgG, IgM, C - reactive
7		protein (CRP), antinuclear antibodies (ANA), inflammatory cytokines and adipokines (interleukin
8		1- β (IL-1 β), interleukin 6 (IL-6), interleukin 8 (IL-8), monocyte chemotactic protein-1 (MCP-1),
9		tumor necrosis factor α (TNF α), leptin, adiponectin, resistin, plasminogen activator inhibitor-1
10		(PAI-1).
11	10	Higher prevalence of autoimmune diseases such as ulcerative colitis, rheumatoid arthritis, lupus,
12		and multiple sclerosis.
13		
14	2.6 Int	ended Use of Study Findings
14	2.0 m	
15	Given t	hat epidemiological research on the health effects of drinking water exposures to PFAS other than
16	PFOA i	s at an early stage, the Multi-site Study should make an important contribution to the scientific

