and average PFAS serum levels. The primary analyses will evaluate each PFAS chemical separately; sum

of PFAS measures may also be considered. Statistical analyses using prevalent cases in a cohort design 1 2 which takes into consideration the times of diagnosis will also be conducted. ATSDR will explore the use 3 of methods for evaluating multi-pollutant mixtures, such as the hierarchical Bayesian model, to analyze 4 the effects of exposures to the PFAS mixtures. ATSDR will use quantitative methods to assess the impact 5 of possible selection bias and possible confounding due to unmeasured risk factors (Lash 2009). There 6 are several caveats and recommendations in conducting analyses of mixtures to determine the optimal 7 method that avoids amplifying bias due to confounding (Weisskopf et al 2018). For the bias analyses, ATSDR will identify "negative control" diseases with no known association with PFAS exposures (Lipsitch 8 9 2010). ATSDR conducted a literature search to identify these negative control diseases and included them 10 in the questionnaire.

ATSDR will interpret the findings from this study based on the magnitude of the effect estimates (e.g., the linear regression coefficient for continuous outcomes or the odds ratio for categorical outcomes) of the exposure-response relationship, consistency with findings from other studies, and the possible sources of bias (Rothman 2014). The analyses will construct confidence intervals to indicate the level of precision (or uncertainty) in the effect estimates.

The studies will use statistical significance testing to interpret findings but will not use it as a sole factor in determining scientific and public health significance (Rothman et al. 2008, 2010; Stang et al. 2010). A finding that fails to achieve statistical significance can still provide evidence for a causal association, and a finding that achieves statistical significance can lack any such significance (Porta 2014).

20 4. RESULTS REPORTING

21 4.1 Notification of Individual Results

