- ____No, it is irregular
- ____No, she does not have a period \rightarrow go to Question F10
- ____Don't know \rightarrow go to Question F10

F7. How many days has been your daughter's cycle on average during the last year?

____>26 days

- ____27-29 days
- ____30-32
- ____>32 days
- ____Don't know

F8. Can you characterize your daughter's usual period flow during the last year?

- ___Light
- ____Medium
- ____Heavy
- ____Don't know

F9. When was your daughter's last period before this study blood draw?

Date:__

____Don't know

F10. Has your daughter ever been pregnant?

____Yes

____No \rightarrow go to Section F

____Don't Know \rightarrow go to Section F

____Refused to answer \rightarrow go to Section F

F11. How many times has your daughter been pregnant?

	Pregnancy #1	Pregnancy #2	Pregnancy #3
a. What month and year did this pregnancy start?	/	/	/
b. What month and year did this pregnancy end?	/	/	/
c. Did the pregnancy result in a live birth?	Yes	Yes	Yes
	No (go to g)	No (go to g)	No (go to g)
	Don't Know	Don't Know	Don't Know
d. Did your daughter breastfeed the child?	Yes	Yes	Yes
	No (go to g)	No (go to g)	No (go to g)
	Don't Know	Don't Know	Don't Know
e. How long did your daughter breastfeed the child?	months	months	months
f. When did your daughter stop breastfeeding the			
child?	monthyear	monthyear	monthyear
g. Did a doctor or nurse say that your daughter had	Yes	Yes	Yes
pre-eclampsia during her pregnancy?	No	No	No
	Don't know	Don't know	Don't know
h. Did a doctor or nurse say that your daughter had	Yes	Yes	Yes
pregnancy-induced hypertension?	No	No	No
	Don't know	Don't know	Don't know
i. Did a doctor or nurse say that your daughter had	Yes	Yes	Yes
gestational diabetes?	No	No	No

Don't know	Don't know	Don't know

Section G. Mother's Pregnancy History

Starting with the pregnancy of your child in this study (Pregnancy 1), and including up to three of [your/the birth mother's] previous pregnancies, please fill out the table below. Circle the appropriate response.

	Pregnancy 1	Pregnancy 2	Pregnancy 3	Pregnancy 4
a. What month and	/	/	/	/
year did this				
pregnancy start?				
b. What month and	/	/	/	/
year did this				
pregnancy end?	Voc	Voc	Voc	Voc
c. Did the pregnancy	res	res	res	res
	No (go to g)	No (go to g)	No (go to g)	No (go to g)
	Don't Know	Don't Know	Don't Know	Don't Know
d. Did [you/the	Yes	Yes	Yes	Yes
child's mother]	No \rightarrow go to Part j.	No \rightarrow go to Part j.	No \rightarrow go to Part j.	No \rightarrow go to Part j.

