ATSDR estimates the average public reporting burden for this collection of information as 20 minutes per response, including the time for reviewing instructions, searching existing data/information sources, gathering and maintaining the data/information needed, and completing and reviewing the collection of information. An agency may not conduct or sponsor, and a person is not required to respond to a collection of information unless it displays a currently valid OMB Control Number. Send comments regarding this burden estimate or any other aspect of this collection of information, including suggestions for reducing this burden to CDC/ATSDR Information Collection Review Office, [name]; ATTN: PRA (0923-xxxx)).

Medical Record Abstraction Form - Adult

Study ID: []	Participant Name: []	Date of Birth:///	SSN: xxx-xx-xxxx
--------------	----------------------	-------------------	------------------

The person named above, or his or her legal representative, has authorized you to release his or her medical records to ATSDR/[institution name] for research purposes. Please check If you have a record that a doctor or other health care provider diagnosed or is treating any of the following medical conditions.

Please fill out the table below. Circle appropriate response and specify requested details as directed. Thank you.

Medical Condition	Record Located (Comments)	Year of Diagnosis or Treatment
a. High cholesterol?	Yes No	
b. Other dyslipidemia?	Yes (Please specify diagnosis) No	
c. Heart disease?	Yes No	
d. Hypertension?	Yes No	
e. Pregnancy induced hypertension?	Yes No	
f. Thyroid disease?	Yes (Please specify diagnosis) No	

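### Cycle-length options on both child questionnaires overlap and omit short cycles, and the adult autoimmune record item lists two non-autoimmune conditions with one shared year

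*Protocol*

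**What the plan says.** **Cycle length.** Question F7 appears in identical form in Attachment 15 (child long form) and Attachment 15a (child short form). It asks about the daughter's "cycle on average during the last year". The printed options are more than 26 days, 27 to 29, 30 to 32, more than 32, and don't know. Section 3.9 includes menstruation among the elimination routes the recipient should try to build into the serum modelling, and lists cycle length among the details the questionnaires collect. Section 3.10 makes estimated cumulative serum level the primary exposure.

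**Autoimmune disease.** Item n of Attachment 17a reads "n. Autoimmune disease? (i.e. Lupus, Multiple sclerosis, Emphysema, Fibromyalgia", and the list ends with celiac and Crohn's disease. Its answer field is "Yes (Please specify) No", and the form has one column headed "Year of Diagnosis or Treatment", so the row has one year cell. Ulcerative colitis and rheumatoid arthritis have their own rows, l and m. Adult hypothesis 10 in section 2.5.2 begins "Higher prevalence of autoimmune diseases such as ulcerative colitis, rheumatoid arthritis, lupus" and goes on to multiple sclerosis. Section 3.10 plans "Statistical analyses using prevalent cases in a cohort design" "which takes into consideration the times of diagnosis will also be conducted". Section 3.6.5.2 uses the record review to confirm conditions reported in the adult questionnaire.

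**The concern.** Each item, followed as printed, can collect something other than what it is meant to collect.

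In F7, the first option looks like a reversed inequality sign. The list then neither covers all cycle lengths nor separates them, so a parent may have no correct box or two.

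In item n, the list is introduced by i.e., which tells the provider what counts. Emphysema is a lung disease and fibromyalgia a pain condition. Neither is named in hypothesis 10, yet a provider following the form would circle yes for either. Lupus and multiple sclerosis, which hypothesis 10 does name, share one row and one year cell with four other conditions, although an analysis by time of diagnosis is planned. At stake are the usability of one input to the exposure model for some girls, and the clarity of the record-confirmed autoimmune diagnosis and its date.

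**Working it through.** **F7.** The only inputs are the printed options, which are the same on both child forms. Each whole-day cycle length from 21 to 40 was assigned to every option it satisfies:

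| Cycle length (days) | Options satisfied | Count |
|---|---|---|
| 21 to 26 | none | 0 |
| 27 to 29 | more than 26; 27 to 29 | 2 |
| 30 to 32 | more than 26; 30 to 32 | 2 |
| 33 to 40 | more than 26; more than 32 | 2 |

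No length fits exactly one option. A tick on the first box could come from any cycle of 27 days or more, or from a parent who read it as meaning short cycles. The three other boxes will also miss girls whose parents ticked the first. The neighbouring questions do not recover the length: F6 asks regularity, F8 flow, and F9 the date of the last period. F7 has no free text.

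If less than 26 was intended, exactly 26 days would still have no box. With 26 days or fewer as the first option, every length from 21 to 40 falls in exactly one category.

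**Item n.** The document states no figure to reproduce, so the passages are set side by side:

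| Condition | Named in hypothesis 10 | Own row and year on the adult form |
|---|---|---|
| Ulcerative colitis | yes | yes (l) |
| Rheumatoid arthritis | yes | yes (m) |
| Lupus | yes | no (n, shared) |
| Multiple sclerosis | yes | no (n, shared) |
| Celiac disease, Crohn's disease | no | no (n, shared) |
| Emphysema, fibromyalgia | no | no (n, shared) |

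Two consequences follow:

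- A yes at item n identifies an autoimmune disease only if the specify field is completed and read.
- If a participant has two or more of the six conditions, one year cannot be assigned to a disease, because the specify field does not ask for a second year.

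The child record form (Attachment 17b) already gives lupus and celiac disease separate rows.

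**The case against.** **Item n.** The answer field asks the provider to specify the disease, so an analyst can drop emphysema and fibromyalgia. The letter in Attachment 17 says the study team may review records in the provider's office. Section 3.6.5.2 says the adult questionnaire asks the date of diagnosis for each reported disease, so the record form is not the only source of timing. Nothing makes a bare yes the study's autoimmune outcome. All of this stands. It leaves reliance on a completed free-text field, and ambiguity in the record-verified year for participants with several listed conditions.

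**F7.** Section 3.9 says the recipient should attempt to integrate a broad set of factors and fixes no model input. The item reaches only menstruating girls. This also stands and limits the effect, but it does not make the options usable.

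**A stronger reading.** A reader might infer that item n swamps the autoimmune outcome and biases it toward the null. Attachment 3b gives lupus 0.2% and multiple sclerosis 0.32%, so 6,000 adults yield 6,000 × 0.002 = 12 and 6,000 × 0.0032 = 19.2 cases, about 31. Assuming that emphysema and fibromyalgia together affect 2% to 5% of adults would add 120 to 300, or 4 to 10 times as many. The document does not support this, for four reasons:

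- It gives no prevalence for either condition.
- The dilution arises only if the free text is left blank or ignored.
- The comparison omits ulcerative colitis (6,000 × 0.005 = 30) and rheumatoid arthritis (6,000 × 0.012 = 72), which have their own rows. Against all four named diseases, 31.2 + 30 + 72 = 133.2, the same assumption gives 120/133.2 = 0.9 to 300/133.2 = 2.3 times.
- Bias toward the null also requires that the added conditions be unrelated to exposure.

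Section 3.3.2 already says 6,000 adults is too small for other autoimmune diseases.

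**Conclusion.** Both items are wrong as printed; the consequences are modest.

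The F7 defect is certain. No cycle length maps to a single option, and the answers cannot be repaired after collection. It affects menstruating girls in the child study, for a variable section 3.9 says is collected for serum reconstruction. The adult questionnaire (Attachment 16) is not in the text available here, so nothing is claimed about adult women.

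Item n does not necessarily yield wrong data. It invites non-autoimmune confirmations that only a completed specify field can undo, and it leaves the verified year unassignable for anyone with more than one of the six conditions. No size of bias can be derived from the document, and none is asserted. This is a minor correction, worth making because it costs almost nothing before data collection.

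**What to change.** 1. In F7 of Attachments 15 and 15a, change the first option to 26 days or fewer. The four categories are then mutually exclusive and cover all lengths.
2. In Attachment 17a, take emphysema and fibromyalgia out of item n; if they are wanted, list them on separate lines.
3. Give lupus, multiple sclerosis, celiac disease and Crohn's disease their own yes/no and year, as rows l and m already do for ulcerative colitis and rheumatoid arthritis.

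The cost is one changed option on two questionnaires and a few more lines for the provider. The forms still carry placeholder clearance numbers, so the edits can be made before they are finalised.

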Attachment 17b.

Medical Condition	Record Located (Comments)	Year of Diagnosis or Treatment
g. Delayed puberty?	Yes (Please specify diagnosis) No	
h. Obesity?	Yes No	
i. Lupus	Yes No	
j. Celiac disease	Yes No	
k. Diabetes type 1	Yes No	
I. Diabetes type 2 Yes No		
m. Attention deficit hyperactivity disorder (ADHD) or attention	Yes (Please specify diagnosis) No	
n.Other learning or behavioral problems?	Yes (Please specify diagnosis) No	
o. Cancer?	Yes (Please specify diagnosis)No	
o. Other cancer?	Yes (Please specify diagnosis) No	

Multi-site Study

Form Approved OMB No. 0923-XXXX Exp. Date xx/xx/201x

Child/Parent Neurobehavioral Test Battery

ATSDR estimates the average public reporting burden for this collection of information as 90 minutes per child response and 15 minutes per parent response, including the time for reviewing instructions, searching existing data/information sources, gathering and maintaining the data/information needed, and completing and reviewing the collection of information. An agency may not conduct or sponsor, and a person is not required to respond to a collection of information unless it displays a currently valid OMB Control Number. Send comments regarding this burden estimate or any other aspect of this collection of information, including suggestions for reducing this burden to CDC/ATSDR Information Collection Review Office, [name]; ATTN: PRA (0923-xxxx).

Proprietary Neurobehavioral Test Information

The following test forms are not found in the ATSDR Multi-site PFAS Health Study Protocol (Number XXXX). The data collection forms are copyrighted and may be reproduced only with written permission from the publishers. The SDQ allows paper versions of its forms to be reproduced and used provided ATSDR does not charge any fee to participants.

To review a copy of the test forms, write to the publishers at the addresses provided below:

Wechsler Abbreviated Scale of Intelligence – 2nd Edition (WASI - II)	Pearson Education, Inc. (Clinical Assessment Ordering Department, [name]) Toll-free: [contact]
A Developmental NEuroPSYchological Assessment – Second Edition (NEPSY-II)	Pearson Education, Inc. (Clinical Assessment Ordering Department, [name]) Toll-free: [contact]
Conners Kiddie Continuous Performance Test, 2 nd Edition (Conners K-CPT 2)	Multi-Health Systems Inc. ([name]) Toll-free: [contact]
Conners Continuous Performance Test 3 rd Edition (CPT 3)	Multi-Health Systems Inc. ([name]) Toll-free: [contact]
Strengths and Difficulties Questionnaire [®] (SDQ [®])	Development and Well-Being Assessment (DAWBA). Feedback and enquiries welcome at [contact] The SDQ is part of the DAWBA family of mental health measures. COPYRIGHT NOTICE: Please note that Strengths and Difficulties Questionnaires, whether in English or in translation, are copyright documents that are not in the public domain . As such, they may not be modified in any way (e.g. changing the wording of questions, adding questions or administering only subsets of questions). This is to ensure that the SDQ is fully comparable across studies and settings. Similarly, to ensure high quality and consistency, unauthorized translations are not permitted. Paper versions may be downloaded and subsequently photocopied without charge by individuals or non-profit organizations provided they are not making any charge to families. Users are not permitted to create or distribute electronic versions for any purpose without prior authorization from youth in mind . If you are interested in making translations or creating electronic versions you MUST first contact [contact] .
Behavior Rating Inventory of Executive Function® (BRIEF®)	Psychological Assessment Resources, Inc. ([name]) Toll-free [contact]
Behavior Rating Inventory of Executive Function [®] – Preschool Version (BRIEF [®] -P)	Psychological Assessment Resources, Inc. ([name]) Toll-free [contact]

Pease Study Neurobehavioral Test Battery for Children

Neurobehavioral Test	Domain	Age	Administration	Time to Administer
Wechsler Abbreviated Scale of Intelligence – 2 nd Edition (WASI - II) Two Subtest Form (FSIQ-2) (Vocabulary and Matrix Reasoning)		6 – 17*	Child	15 minutes
	Auditory Attention and Response Set* (reduced attention)	5 – 16	Child	7 – 11 minutes
	Inhibition*	5 - 16	Child	8 – 11 minutes
	Comprehension of Instructions* (receptive language, trouble following multi-step commands)	4 - 16	Child	6 – 8 minutes
A Developmental	Speeded Naming* (expressive language, processing speed)	4 - 16	Child	2 – 7 minutes
Assessment -2^{nd} edition	Word List Interference* (verbal memory)	7 – 16	Child	6 – 8 minutes
* from Core Assessment	Narrative Memory* (comprehension, verbal memory)	4 - 16	Child	6 – 11 minutes
* from Core Assessment	Design Copying* (visuospatial processing)	4 - 16	Child	7 – 10 minutes
	Theory of Mind (social perception)	4 - 16	Child	10 – 13 minutes
	Sentence Repetition (verbal memory)	4 – 6	Child	4 minutes
	Statue (inhibitory control)	4 – 6	Child	3 minutes
	Word Generation (expressive language, executive control)	4 - 16	Child	4 – 6 minutes
Conners Kiddie Inattentiveness, Impulsivity, Sus Continuous Performance Inattentiveness, Impulsivity, Sus Test, 2 nd Edition Attention, Vigilance (Conners K-CPT 2) Imattentiveness		4-7	Child	8 minutes
Conners Continuous Performance Test 3 rd edition (CPT 3) Inattentiveness, Impulsivity, Sustained Attention, Vigilance		8-17	Child	14 minutes
Strengths and DifficultiesDouble-sided form with impactQuestionnaire [©] (SDQ [©])supplement (behavioral problems)		4 - 17	Parent about Child	5 minutes
Behavior Rating Inventory of Executive Executive Function Function [®] (BRIEF [®])		6-17	Parent about Child	10 minutes
Behavior Rating Inventory of Executive Function® – Preschool Version (BRIEF®-P)		4-5	Parent about Child	10 minutes

Neuropsych	Neuropsychological Test Battery, Children aged 4-17 years			
Age Range, vears	Test	Domains		
6-17 years	Wechsler Abbreviated Scale of Intelligence [®] - Second Edition (WASI [®] - II)	https://www.pearsonclinical.com/psychology/products/1000000 37/wechsler-abbreviated-scale-of-intelligencesecond-edition- wasi-ii.html Author: David Wechsler Qualification Level: C Age Range: Individuals 6:0–90:11 Completion Time: Two-subtest form (Vocabulary and Matrix Reasoning), 15 minutes Scores/Interpretation: FSIQ–2 score: Estimate of general cognitive ability Scoring Options: Manual scoring Publication Date: 2011		
4-16 years	A Developmental NEuroPSYchological Assessment – 2 nd Edition (NEPSY-II)	https://www.pearsonclinical.com/psychology/products/1000005 84/nepsy-second-edition-nepsy-ii.html https://images.pearsonclinical.com/images/Products/NEPSY- II/Clin Chp Author(s): Marit Korkman, Ursula Kirk, Sally Kemp Qualification Code: CL1 Age Range: 3 years to 4 years; 5 years to 16 years Administration: Core Assessment 45 minutes for preschool ages, 1 hour for school ages; Comprehensive Assessment - 90 minutes for preschool ages, 2-3 hours for school ages Publication Year: 2007 This NEPSY-II battery covers Five of Six Domains Executive Functioning/Attention, Language, Memory and Learning, Visuospatial Processing, Social Perception. Sensorimotor Functioning will not be tested. ATTENTION AND EXECUTIVE FUNCTIONING 1) Auditory Attention and Response Set (AA - 5-16 years; RS - 7-16 years). Auditory Attention is designed to assess selective auditory attention and the ability to sustain it (vigilance). Response Set is designed to assess the ability to shift and maintain a new and complex set involving both inhibition of previously learned responses and correctly responding to matching or contrasting stimuli. The child listens to a series of wo		

	body position with eyes closed during a 75-second period and to
	inhibit the impulse to respond to sound distracters.
	LANGUAGE
	1) Comprehension of Instructions (CI – 3-16 years). This subtest is
	designed to assess the ability to receive, process, and execute
	oral instructions of increasing syntactic complexity. For each item,
	the child points to appropriate stimuli in response to oral
	instructions.
	2) Speeded Naming (SN – 3-16 years). This timed subtest is
	designed to assess rapid semantic access to and production of
	names of colors, shapes, sizes, letters, or numbers. The child is
	shown an array of colors and shapes; colors, shapes, and sizes; or
	letters and numbers. He or she names them in order as quickly as
	possible.
	3) Word Generation (SN – 3-16 years). This subtest is designed to
	assess verbal productivity through the ability to generate words
	within specific semantic and initial letter categories. The child is
	given a semantic or initial letter category and asked to produce as
	many words as possible in 60 seconds.
	MEMORY AND LEARNING
	1) Word List Interference (WI – 7-16 years). This subtest is
	designed to assess verbal working memory, repetition, and word
	recall following interference. The child is presented with two
	series of words and asked to repeat each sequence following its
	presentation. Then, he or she recalls each series in order of
	presentation.
	2) Narrative Memory (NM – 3-16 years). This subtest is designed
	to assess memory for organized verbal material under free recall,
	cued recall, and recognition conditions. The child listens to a story
	and is then asked to repeat the story. The child is then asked
	questions to elicit missing details from his or her recall of the
	story.
	3) Sentence Repetition (SR – 3-6 years). This subtest is designed
	to assess the ability to repeat sentences of increasing complexity
	and length. The child is read a series of sentences and asked to
	recall each sentence immediately after it is presented.
	VISUOPSPATIAL PROCESSING
	1) Design Copying (DC – 3-16 years). This subtest is designed to
	assess motor and visual-perceptual skills associated with the
	ability to copy two-dimensional geometric figures. The child
	copies figures displayed in the Response Booklet.
	SOCIAL PERCEPTION
	1) Theory of Mind (3-16 years). This subtest is designed to assess
	the ability to understand mental functions such as belief,
	intention, deception, emotion, imagination, and pretending, as
	well as the ability to understand that others have their own
	thoughts, ideas, and feelings that may be different from one's
	own and the ability to understand how emotion relates to social
	context and to recognize the appropriate affect given various
	social contexts. In the Verbal task, the child is read various
	scenarios or shown pictures and is then asked questions that
	require knowledge of another individual's point of view to answer
	correctly. In the Contextual task, the child is shown a picture
	depicting a social context and asked to select a photograph from

		four options that depicts the appropriate affect of one of the people in the picture
		https://www.mhs.com/MHS-Assessment?prodname=kcpt2
4-7 years	Connors Kiddie Continuous Performance Test Second Edition™ (Conners K-CPT 2™)	Overview The Conners Kiddie Continuous Performance Test 2 nd Edition™ (Conners K-CPT 2™) assesses attention deficits in children ages 4 to 7 years old. Based on the well-established Conners CPT paradigm, the Conners K–CPT 2 takes only half the time (7.5 minutes) to complete, making it more appropriate for younger children. Results from the measure can be used for clinical assessment, early identification, and educational classification. The assessment can be also be used to evaluate treatment effectiveness by administering the test before treatment and during treatment to monitor change. Author(s): [name] Key Areas Measured: Inattentiveness Impulsivity Sustained Attention Vigilance Age: 4 to 7 Administration Type: Self Administration Time: 7.5 Minutes Qualification Level: B
8-17 years	Connors Continuous Performance Test Third Edition™ (CPT 3™)	https://www.mhs.com/MHS-Assessment?prodname=cpt3 Overview The Conners Continuous Performance Test Third Edition™ (Conners CPT 3™) measures attention-related problems in individuals aged eight years and older. By indexing the respondent's performance in areas of inattentiveness, impulsivity, sustained attention, and vigilance, the Conners CPT 3 can aid in the assessment of Attention-Deficit/Hyperactive Disorder (ADHD) and other neurological conditions related to attention. The Conners CPT 3 provides objective information about an individual's performance in attention tasks, complementing information obtained from rating scales such as the Conners 3®. New Scores and Score Dimensions of Attention Measured: Inattentiveness Impulsivity Sustained Attention Vigilance Key Areas Measured: Inattentiveness Impulsivity Sustained Attention Vigilance Age: 8+ Administration Type: Self Administration Time: 14 Minutes

		Qualification Level: B
		http://www.cebc4cw.org/assessment-tool/strengths-and- difficulties-questionnaire/
